14.4 Criteria for stopping study

The study will be discontinued if 25-30% of patients are unable to complete surgery due to toxicity. Analysis will be conducted after the first 20 patients are enrolled onto the study. If >6 patients are not able to proceed with surgery due to excessive toxicity the study will discontinue due to unacceptable toxicity.

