1.1 Rationale for neoadjuvant therapy in PDAC

Several lines of evidence support a neoadjuvant approach in the treatment of patients with pancreatic cancer (7). This is based on the rationale that 70-80 % of patients who undergo resection with curative intent still experience relapse shortly after their recovery; perhaps neoadjuvant therapy might spare these patients with an aggressive biology a surgery that may not alter the course of their disease (8). Additionally, neoadjuvant chemotherapy provides the opportunity to evaluate response to therapy “*in vivo*”, and spares patients with poor biology a

large and potentially morbid operation. Prior to FOLFIRINOX (RR: 31%) and nab-paclitaxel/gemcitabine (RR: 23%), the response rate to gemcitabine as a single agent was reported to be in a range of 6-7 %, which was unlikely to result in a meaningful R0 resection rate. Additionally, up to one-third of patients who undergo surgical resection may not recover well enough to undergo adjuvant therapy; therefore, ensuring adequate treatment in the form of neoadjuvant therapy theoretically results in better delivery of therapy.

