9. STUDY PROCEDURES

9.1 EUS or CT-Guided Biopsy Procedure

Pancreatic cancer is commonly staged by the means of endoscopic ultrasound (EUS). This is a standard of care procedure which includes minimal sedation and upper endoscopy. A linear echoendoscope will be utilized to identify the pancreatic mass. A fine needle aspirate (FNA) or core biopsy will be performed at the same time. As with standard practice, biopsy will be performed with on-site cytology review to confirm malignancy. All diagnostic biopsies must be reviewed by the Pathology Department per the institutional guidelines.

If patients do not proceed to surgery after neoadjuvant treatment (may occur if the patient refuses surgery, is not eligible for surgery or has progression of disease), then an optional biopsy may be completed at the end of treatment. In these cases, a CT-guided biopsy will likely be performed. EUS biopsies are typically performed for patients who have localized disease while CT-guided biopsy is typically performed when metastatic disease is suspected.

Biopsies may be performed prior to patient enrollment as they are standard of care for pancreatic cancer diagnosis. Therefore, tissue samples being stored with the Pathology Department (i.e. archival tissue) in lieu of fresh tissue collection may be requested after enrollment to satisfy the baseline tissue collection requirement of this study. Additionally, it may be difficult to coordinate fresh tissue collect at the time of surgical resection (see below) or biopsy; therefore, archival tissue may also be collected to satisfy the post-neoadjuvant treatment tissue collection requirement of this study.

Additional details regarding tissue collection can be found in Section 12.1.

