14.3 Statistical analysis plan

Primary Outcome:

- Pathologic complete response: the proportion of the 48 patients having a pathologic complete response with a 95% confidence interval (using normal approximation) will be calculated.

Secondary Outcomes:

- *Safety:* Adverse events of grades 3, 4, 5 by the CTCAE v4.3 criteria for each category listed in section 2.1.6 will be summarized. The proportion of patients with each category of AE will be calculated with a 95% confidence interval. After the enrollment of the first 20 patients, we will evaluate the rate of surgical resection. If >6 patients are not able to proceed with surgery due to excessive toxicity or progression (not including occult metastatic peritoneal disease that was found during surgery and not on imaging) the study will discontinue due to unacceptable toxicity.

- *Ability of patients to undergo surgical resection after receiving neoadjuvant FOLFIRINOX*: the proportion of patients who are able to go through surgery among those who have resectable tumor will be calculated accompanied with a 95% confidence interval.
- *Rate of resectability* will be evaluated by determining the proportion of patients who are able to undergo surgery with resection of their primary tumor (R0 vs R1) resection. A 95% confidence interval will be constructed for the rate.
- *Disease free survival (DFS)*: DFS is defined as time from registration to evidence of tumor recurrence (including clinical deterioration related to the underlying pancreatic cancer, as assessed by the investigator) or death from any cause. Kaplan-Meier curve for DFS will be plotted. Median DFS time will be calculated accompanied with a 95% confidence interval.
- *Overall survival*: time from registration to death for 48 patients with right censoring will be analyzed using Kaplan-Meier estimate. Median survival time will be obtained accompanied with a 95% confidence interval.
- *Objective response rate*: proportion of patients with complete responses (CR) or partial responses (PR) after 4 cycles of FOLFIRINOX treatment will be constructed with a 95% confidence interval.
- *Disease control rate*: Proportion of patients with complete responses (CR), partial responses (PR), or stable disease (SD) after 4 cycles of FOLFIRINOX treatment will be obtained with a 95% confidence interval.

Tertiary Outcomes:

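### The only numeric study-level stopping rule is stated inconsistently: 25-30% does not match more than 6 of 20, and Sections 14.3 and 14.4 count different events

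*Combined protocol and SAP*

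**What the plan says.** Section 14.4 (Criteria for stopping study) gives the rule twice. As a percentage: "The study will be discontinued if 25-30% of patients are unable to complete surgery due to toxicity". As a count: "Analysis will be conducted after the first 20 patients are enrolled onto the study", followed by "If >6 patients are not able to proceed with surgery due to excessive toxicity the study will discontinue due to unacceptable toxicity".

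Section 14.3 (Statistical analysis plan, Safety) sets a rule at the same point: "After the enrollment of the first 20 patients, we will evaluate the rate of surgical resection". Its trigger is "If >6 patients are not able to proceed with surgery due to excessive toxicity or progression". It leaves out occult peritoneal metastasis "that was found during surgery and not on imaging) the study will discontinue due to unacceptable toxicity". Section 14.4 mentions neither progression nor this exclusion.

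Section 17.2 allows the investigators to recommend early closure and the Data Safety Monitoring Committee (DSMC) to impose it, but gives no number. The limits on delays over 14 days in Sections 8 and 11.5 apply to single patients or agents. The rule in 14.3 and 14.4 is therefore the only numeric study-level stopping rule.

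**The concern.** There are two separate conflicts.

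1. **Threshold, within 14.4.** The percentage and the count do not describe the same limit at the one planned look. The two sentences also name different events: one refers to completing surgery, the other to proceeding to it.
2. **Events, between 14.3 and 14.4.** The look, the count and the consequence are the same, but the patients counted are not. Section 14.3 would also label a stop driven mostly by progression as one for unacceptable toxicity.

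Progression before surgery is not a remote case. Section 9.1 lists it among the reasons for not reaching surgery: "may occur if the patient refuses surgery, is not eligible for surgery or has progression of disease".

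At stake is whether enrolment stops after 20 patients. If the text supports either answer on the same data, the choice is made after the data are seen, which a prespecified rule is meant to prevent. Section 17.1 states that the DSMC is not acting as a DSMB for this study, so the written rule carries more weight.

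**Working it through.** **Inputs.** Look at 20 enrolled patients (14.3, 14.4). Limits of 25-30% and more than 6 (14.4); more than 6 (14.3). The documents give no operating characteristics for the rule and no toxicity-failure rate for resectable patients, so every true rate below is an assumption.

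**Step 1: percentage against count.**

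- 0.25 × 20 = 5 and 0.30 × 20 = 6.
- More than 6 means at least 7, and 7/20 = 35%.

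The first sentence of 14.4 names no denominator; 20 comes from the sentence after it. Against the 30% bound, the two statements differ only at exactly 6 failures. Against the 25% bound, they differ at 5 and at 6.

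**Step 2: how often this matters.** Let X be the number of failures among 20, binomial with true rate p: P(X = k) = C(20, k) p^k (1 − p)^(20 − k).

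| True rate p | P(X = 6) | P(X = 5 or 6) | P(X ≥ 6) | P(X ≥ 7) |
|---|---|---|---|---|
| 10% | 0.009 | 0.041 | 0.011 | 0.002 |
| 15% | 0.045 | 0.148 | 0.067 | 0.022 |
| 20% | 0.109 | 0.284 | 0.196 | 0.087 |
| 25% | 0.169 | 0.371 | 0.383 | 0.214 |
| 30% | 0.192 | 0.370 | 0.584 | 0.392 |

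**Step 3: 14.3 against 14.4, both at 7 or more.** Every patient counted under 14.4 is also counted under 14.3. The probability that the sections disagree is therefore P(X ≥ 7 at the combined rate) − P(X ≥ 7 at the toxicity rate). The combined rate is taken as the sum of the two, which assumes that no patient is counted under both causes.

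| Toxicity | Progression | 14.3 stops | 14.4 stops | Disagreement |
|---|---|---|---|---|
| 10% | 5% | 0.022 | 0.002 | 0.020 |
| 10% | 10% | 0.087 | 0.002 | 0.084 |
| 10% | 14% | 0.184 | 0.002 | 0.181 |
| 25% | 5% | 0.392 | 0.214 | 0.178 |
| 25% | 10% | 0.583 | 0.214 | 0.369 |
| 25% | 14% | 0.720 | 0.214 | 0.506 |

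Differences are taken before rounding.

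**Step 4: the one relevant series in the document.** Section 1.3 describes 21 patients on FOLFIRINOX, of whom 2 could not tolerate treatment and 3 progressed. With toxicity 2/21 and the two causes combined 5/21, 14.3 stops with probability 0.178 and 14.4 with 0.002, a gap of 0.176. These patients had borderline resectable or locally advanced disease, and not tolerating treatment is not the same as not reaching surgery, so this is illustration only.

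**Step 5: a concrete case.** Three toxicity failures plus four progressions make 7 of 20. The limit is met under 14.3; under 14.4 the count is 3, far below it.

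**The case against.** The best defence of 14.4 is that 25-30% states a tolerance and that more than 6 of 20, the first count above 30%, puts it into practice. A range cannot itself be a cut-off, and more than 6 is the one count both sections share. But the sentence says the study stops at 25-30%, not above 30%, and 6/20 is exactly 30%. That reading also leaves the event lists unreconciled.

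A second argument is that no sentence orders the study to continue, so all can be obeyed together by acting on whichever trigger is met first. It is true that meeting 14.4's count always meets 14.3's. Yet a stated cut-off normally implies continuing below it, and if all the sentences are independent triggers, the count in 14.4 has no function beside its own lower percentage.

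Third, the larger gaps rest on a 25% toxicity-failure rate that no part of the document supports. This stands. At 2/21, P(X = 6) is only 0.007 and P(X = 5 or 6) is 0.034, so the threshold conflict would seldom arise. The conflict over events remains material at that rate.

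Fourth, monthly investigator and DSMC review under Section 17.2 continues whatever the wording. This stands as mitigation, but that review has no numeric threshold.

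**Conclusion.** The concern holds on both counts, and the rule must be corrected. On the text alone, 6 of 20 toxicity failures (also 5 of 20, if 25% is the trigger) or a suitable mix of toxicity and progression gives different answers depending on which sentence is followed.

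The size depends on the assumed rates. The threshold conflict matters most where the true toxicity-failure rate is near the stated limit and is small at 10% or below. The disagreement between sections runs from 0.02 to 0.18 with 10% toxicity and 5-14% progression, and from 0.18 to 0.51 with 25% toxicity. These figures assume independent patients and no overlap between the two causes of failure. The inconsistency itself rests on none of these rates.

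The primary pathologic complete response analysis is not affected.

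**What to change.** Put one identical rule in 14.3 and 14.4, with one count, its matching percentage and one event list. The sponsor must choose the limit and the events.

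- **Smallest change.** Delete the 25-30% sentence. In both sections, stop if 7 or more of the first 20 enrolled patients (35%) cannot proceed to surgery because of excessive toxicity or progression, keeping 14.3's exclusion of occult peritoneal disease. Give the reason for stopping as failure to reach surgery from toxicity or progression. This leaves 14.3's stop probabilities unchanged but openly accepts a 35% limit.
- **If the intended limit is 30%.** Write 6 or more (30%). The chance of stopping at a true combined rate of 10-15% rises from 0.002-0.022 to 0.011-0.067, and at 24% from 0.18 to 0.34. The count should be chosen with the combined rate in mind.
- **If progression is to be left out.** Section 1.1 offers a reason: "perhaps neoadjuvant therapy might spare these patients with an aggressive biology a surgery that may not alter the course of their disease". Say so in both sections. The rule then becomes less sensitive than the present 14.3: at the Section 1.3 series rates, a toxicity-only limit of 6 stops with probability 0.009, against 0.178.

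In each case, use one term for the surgical event, and state that the look is made once the surgical outcome of all 20 patients is known, as 14.3's reference to the resection rate already implies. The cost is protocol wording and its IRB approval (Section 16). The sample size and the primary analysis do not change.

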15. DATA FORMS AND SUBMISSION SCHEDULE

This study will utilize electronic Case Report Form completion in the OnCore[®] database. A calendar of events and required forms are available in OnCore[®]. The OnCore[®] database is a comprehensive database used by the IUSCC Clinical Trials Office (CTO) and supported by the Indiana Clinical and Translational Sciences Institute (CTSI).

Access to data through OnCore[®] is restricted by user accounts and assigned roles. Once logged into the OnCore[®] system with a user ID and password, OnCore[®] defines roles for each user which limits access to appropriate data. New username and passwords can be obtained by going to the following link: <https://redcap.uits.iu.edu/surveys/?s=sYN36a9U5c>. For further questions regarding your oncore account you can contact the CTO Cancer Center Oncore Support via email at: [contact].

All source documents are to remain in the patient's clinic file. All documents should be kept according to applicable federal guidelines. Clinical trial data in OnCore[®] are periodically monitored by the IU Simon Cancer Center Data Safety Monitoring Committee.

Generally, clinical and correlative data will be electronically captured in OnCore[®]. If procedures on the study calendar are performed for standard of care, at minimum, that data will be captured in the medical record. Select standard of care data will also be captured in OnCore[®], according to study-specific objectives. Please see the OnCore[®] data collection guidelines for further details. Tissues will be stored in the IUSCC and data will be kept in OnCore[®] in a BSM.

16. PATIENT CONSENT AND PEER JUDGMENT

The protocol and informed consent form for this study must be approved in writing by the appropriate Institutional Review Board (IRB) prior to any patient being registered on this study.

Changes to the protocol, as well as a change of principal investigator, must also be approved by the Board. Records of the Institutional Review Board review and approval of all documents pertaining to this study must be kept on file by the investigator (housed in the Clinical Trials Office) and are subject to inspection at any time during the study. Periodic status reports must be submitted to the Institutional Review Board at least yearly, as well as notification of completion of the study and a final report within 3 months of study completion or termination.

The study will be conducted in compliance with ICH guidelines and with all applicable federal (including 21 CFR parts 56 & 50), state or local laws.

17. DATA AND SAFETY MONITORING

17.1 Data Safety Monitoring Committee

The Data Safety Monitoring Committee (DSMC) of the Indiana University Simon Cancer Center (IUSCC) is responsible for patient safety and privacy protection, compliance with required reporting, and study integrity for all trials conducted at IUSCC. Members are subject matter experts from multiple disciplines including medical oncology, pediatrics, biostatistics, behavioral oncology, radiation oncology, urology, surgery, gynecologic oncology, data and project management and research administration who are appointed by the DSMC Chair. The DSMC will provide independent oversight of the clinical trial so that study integrity is assured. However, the DSMC is not serving as a Data and Safety Monitoring Board (DSMB) for this study. The DSMC will meet per the currently approved DSMP, led by the DSMC Chair and Coordinator, and will review all adverse events, monitoring and auditing reports, unanticipated problems and study non-compliance events that require expedited reporting. Meeting minutes will be maintained in the IUSCC Clinical Trials Office (CTO). Specifically the DSMC has the following responsibilities:

- Assessment of the adequacy of trial-specific Data Monitoring and Safety Plan (DSMP) of studies that are not subject to external monitoring, including investigator initiated studies, and establish risk based monitoring determination of trial specific DSMB.
- Review safety data for investigator initiated trials including all adverse events, unanticipated problems and study non-compliance events requiring expedited reporting.
- Conduct routine study monitoring and auditing in compliance with the IUSCC data quality control review process.

17.2 Data and Safety Monitoring Plan

This trial will comply with the current requirements of the Data and Safety Monitoring Plan (DSMP) of the IUSCC. The CTO of the IUSCC will be the Coordinating Center for this phase 2 trial. Investigators will conduct continuous review of data and patient safety. **Monthly review meetings** are required and will include the Principal Investigator, clinical research specialist and/or study nurse (or other members will be present at the Principal Investigator's discretion). **Monthly** meeting summaries should include review of data, the number of patients, significant toxicities as described in the protocol, and responses observed. Summaries will be submitted to [contact] and reviewed monthly by DSMC. **Monthly** meeting summaries will include and document review of data and patient safety by including: the number of patients, significant toxicities as described in the protocol, responses observed, eligibility of patients enrolled at each site, serious adverse events (SAEs) or unanticipated problems (UPs) (both IUSCC and those reported from other institutions), dose adjustments, and protocol deviations. Meeting minutes will be submitted and reviewed by the DSMC.

Study Monitoring for Moderate Risk Trials

All trials conducted at the IUSCC are subject to auditing and/or monitoring. Reports will be reviewed by the full DSMC at the time of study review (Reference Risk Table in full DSMC Charter).

Early Study Closure

At any time during the conduct of the trial, if it is the opinion of the investigators that the risks (or benefits) to the patient warrant early closure of the study, this recommendation should be made in writing to the Data Safety Monitoring Committee. Alternatively, the DSMC may initiate suspension or early closure of the study based on its review.

Reporting Guidelines

The DSMC has streamlined the reporting process by utilizing reports from OnCore[®]. This has allowed direct view of reports within the Clinical Trials Management System (CTMS); thus, discontinuing all paper reports. SAE reports are entered into OnCore[®] monthly and reviewed by the DSMC chair and/or coordinator monthly. Findings will be reported to the full DSMC at the time of the studies DSMC review.

Reporting Death

Death will be captured in the Case Report Form and reported per local IRB reporting guidelines.

Study Accrual Oversight

Accrual data will be entered into the IU Simon Cancer Center OnCore[®] system. The Protocol Progress Committee (PPC) will review study accrual twice per year while the PPC coordinator will review accrual quarterly.

Continuing Review

All Continuing Reviews (CR) will be reviewed annually or as dictated by the Institutional Review Board. Participating sites will submit a copy of the CR with attachments to the IUSCC Multicenter Network Associate Administrator, or designee.

Protocol Deviations

Protocol deviations will be entered into OnCore[®] and reviewed by the DSMC chair and/or coordinator. Findings will be reported to the full DSMC at the time of DSMC review.

Unanticipated Problems

Investigators are required to submit unanticipated problems to the DSMC (through OnCore[®]) concurrent with their submission of them to the IRB. **Prompt** reporting of unanticipated problems to the IRB is defined as within 5 days for on-site studies.

Unanticipated problems that will be reported **promptly** to the IRB include:

- Major protocol deviation/violation
- Change to the protocol taken without prior IRB review to eliminate apparent immediate hazard to a research subject (e.g. purposeful and for subject safety)
- Complaint of a subject that indicates unexpected risks, or complaint that cannot be resolved by the research team

- Publication in the literature, safety monitoring report, interim result or other finding that indicates an unexpected change to the risks or potential benefits of the research, in terms of severity or frequency
- Change in FDA labeling or withdrawal from marketing of a drug, device, or biologic used in a research study
- Investigator- or sponsor-initiated suspension or hold
- Serious or continuing non-compliance
- Adverse events

18. REPORTING ADVERSE EVENTS

18.1 Definitions of Adverse Events

18.1.1 Adverse Event (AE)

An **adverse event** is defined as an unplanned, unwanted medical occurrence associated with the use of a drug in humans, whether or not considered drug related. An adverse event can be **ANY** unfavorable and unintended sign (e.g. an abnormal laboratory finding), symptom, or disease temporarily associated with the use of a medicinal (investigational) product, whether or not considered related to the medicinal (investigational) product (attribution of ‘unrelated’, ‘unlikely’, ‘possible’, ‘probable’, or ‘definite’). An AE may also include a newly occurring event or a previous condition that has increased in severity or frequency since the administration of the investigational product. Adverse events will be graded according to the NCI Common Toxicity Criteria, Version 4.0. A copy of the current CTCAE version 4 is available at <http://ctep.cancer.gov/reporting/>.

18.1.2 Unexpected Adverse Event

An adverse event not mentioned in the Investigator's Brochure or package insert or the specificity or severity of which is not consistent with the Investigator's brochure or package insert.

18.1.3 Unanticipated Problem (UP)

An unanticipated problem is any incident, experience, or outcome that meets all of the following criteria:

- 1) unexpected (in terms of nature, severity, or frequency) given (a) the research procedures are described in the protocol-related documents, such as the IRB-approved research protocol and informed consent document; and (b) the characteristics of the subject population being study;
- 2) related or possibly related to participation in the research; and
- 3) suggests that the research places subjects or others at a greater risk of harm (including physical, psychological, economic, or social harm) related to the research than was previously known or recognized.

Only a small subset of adverse events occurring in human subjects participating in research will meet these three criteria for an unanticipated problem. Furthermore, there are other types of incidents, experiences, and outcomes that occur during the conduct of human subjects research that represent unanticipated problems but are not considered adverse events. For example, some unanticipated problems involve social or economic harm instead of the physical or psychological harm associated with adverse events. In

other cases, unanticipated problems place subjects or others at increased risk of harm, but no harm occurs.

